1. BACKGROUND AND RATIONALE

There are over 1 million people living with spinal cord injury (SCI) with devastating functional impairments including paralysis and bowel/bladder dysfunction.¹ Nearly every person with SCI develops neurogenic bladder.² The gold-standard treatment of neurogenic bladder involves the use of anticholinergic bladder medications, which suffers from non-compliance and adverse medication effects.³ Improving bowel and bladder function is the number one priority that people living with SCI wish to achieve.⁴ Treatments such as bladder neuromodulation with tibial nerve stimulation (TNS), have been shown to improve bladder function in SCI without adverse effects.⁵⁻⁶ Percutaneous TNS (PTNS) is performed using a needle inserted into the skin to direct the electric current, provided by trained healthcare workers in the clinic setting under physician supervision. This requires frequent visits in a population with known accessibility challenges. Transcutaneous TNS (TTNS) accomplishes the same goal, but uses non-invasive surface electrodes. However, this modality has only been performed in the clinic setting. There is currently a gap in our knowledge about the safety and feasibility of TTNS at home for bladder neuromodulation in SCI. The proposed research is innovative, in our opinion, because it represents a substantive departure from the status quo by using TTNS at home to replace anticholinergic medications and provide a dignified treatment that can improve quality of life.

Electric stimulation is routinely being used in neurorehabilitation. The PI has published reviews on the current state of rehabilitation in SCI, describing the use of FES and NMES in SCI for motor/sensory recovery, decreasing spasticity, and improving neuropathic pain.⁷⁻⁹ Patients are routinely prescribed electric stimulation units for home use to help with motor recovery and strengthening. We propose the development of a protocol that uses the same equipment in a novel way to affect bladder function. We have tested this in 2 pilot trials and published the results of the first.¹⁰

1. General Introduction

The management of NLUTD in SCI includes: maintaining continence via timed voiding, catheterization (intermittent or indwelling), use of OAB medications, chemodenervation, and/or surgery. While these approaches have dramatically improved morbidity and mortality related to the upper urinary tracts, they are also associated with significant functional impairment¹¹, challenges to community re-entry¹²⁻¹⁴, expense^{14 15}, adverse effects^{11 14}, and ultimately QOL¹¹ (see Table 1).

We propose a **non-invasive, readily-available, and inexpensive** approach that can be **used at home** (and reduces reliance on the health care system) to improve bladder-related health and function, while overcoming existing barriers: **TTNS (transcutaneous tibial nerve stimulation)**, the transcutaneous adaptation of PTNS (percutaneous TNS). PTNS has demonstrated equal efficacy to newer OAB medications in a randomized control trial of 100 SCI subjects, while boasting fewer adverse events.⁶ Although a large study of this nature has not been performed with TTNS in SCI, in the population of people with NLUTD due to Multiple Sclerosis (MS), TTNS has been shown to improve urinary urgency in more than 80% of the subjects, reduce urinary frequency, and had a positive impact on QOL measures.¹⁶

Table 1. Limitations of current treatment approaches to NLUTD

		Pharmacologic		
Limitation	Bladder Management	OAB medications	Chemo-denervation	Neuromodulation (NM)
Side Effects	Functional limitations vary by bladder management method (i.e., incontinence between caths, supply management, hand function, etc.)	Sedation, dry mouth, constipation, etc. Increased risk of dementia Interaction with other medications	Urinary tract infection Change in bladder management may be necessary	Surgical complications with sacral NM
Non-Compliance		Higher doses required in SCI	Requires urologic procedure every 3-6 months	PTNS > 55% non-compliance
Access/ Expense		Newer medications with decreased side effects are often not covered by insurance or are too expensive	Largely unavailable, very expensive, involves invasive procedure.	Both PTNS and sacral NM largely unavailable and very expensive

The Stamobil + is an electric stimulation unit used for the rehabilitation of those with paralysis. It is currently used at TIRR Memorial Hermann on nearly every patient with paralysis for the purposes of motor and sensory recovery. We have used the proposed TTNS protocol for research purposes (HSC-MS-15-0806, HSC-MS-17-0423). Based on the pilot safety data, we believe we should test the efficacy of the protocol for home use in a randomized control trial. The proposed protocol is using the device in a new way, to stimulate the nerves of the legs which is known to effect the bladder in a process described as “neuromodulation.”

Electric stimulation is currently being used in neurorehabilitation. The candidate has published reviews on the current state of rehabilitation in SCI, describing the use of FES and NMES in acute SCI for motor/sensory recovery, decreasing spasticity, and improving neuropathic pain.^{9, 10} Patients are routinely prescribed electric stimulation units for home use to help with motor recovery

and strengthening. We propose the development of a protocol that uses the same equipment in a novel way to effect bladder function.

2. Rationale and justification for the Study

We have selected a neuromodulation technique, TTNS, which we have used safely with evidence of efficacy.

Pilot Data: The **leading theory** for the **mechanism of bladder neuromodulation** by TNS is that stimulation of the tibial nerve sensory afferents block the visceral bladder afferents at the level of the spinal cord.¹⁷ This leads to a disruption of the bladder reflex arc, thereby decreasing motor efferent activity and subsequent pathologic reflex bladder contractions. This reflex arc is intact in people with thoracic level 9 (T9) injury and above (rostral). This hypothesis has been tested in a pilot trial of TTNS in acute SCI.¹⁰

Pilot Trial I. Safety and Bladder Capacity: TTNS in acute SCI was performed in a randomized sham-control trial of TTNS for 30 minutes x 10 days using a commercially/readily available neuromuscular electric stimulation (NMES) device. In this trial, there were no safety events, compliance was 100%, and hospital staff noted ease of use. Decrease in bladder capacity and detrusor-sphincter dyssynergia (DSD) events were both mitigated in the TTNS group (**Fig. 1**). Also, evidence of the proposed mechanism was seen with significantly increased volumes to sensation in the TTNS group compared to the controls post-trial. These findings suggest that TTNS has the potential to **mitigate the development of morbid neurogenic bladder** in acute SCI. We also provided evidence of altering the nervous system response to bladder filling in a cohort of these subjects, suggesting the ability of reducing AD.¹⁸ We then investigated home use of TTNS as the next phase of study.

[figure not shown]

Fig. 1: Bladder sensation, detrusor-sphincter dyssynergia (DSD) frequency and bladder capacity changes in control and TTNS group over time. € between group difference $p=0.01$; *change from baseline $p<0.02$;

Pilot Trial II. Effect on Voiding Program and QOL: TTNS in the home setting was tested in a single-arm pre-post pilot trial in subjects with chronic SCI performing intermittent catheterization (IC) with complaints of incontinence. There was 100% (16/16) completion of trial, no complications, TTNS was found to be easy to use, 86% (12/14) reduced their OAB medication dosage and anticholinergic side effects, and QOL scores improved (**Fig. 2**). This pilot trial suggests TTNS is feasible and safe to be performed at home. A randomized sham-control trial is needed to determine if TTNS can be used at home to manage NGB symptoms, as proposed in this study.

[figure not shown]
[figure not shown]

Fig 2. Incontinence QOL (I-QOL) and Anti-cholinergic Side Effect Questionnaire results. **A.** Baseline and Post-Trial Results of I-QOL total and subscores: A&L= avoidance and limitation; PS= psychosocial; SE= social embarrassment. Δ = change in scores from baseline to post-trial. **B.** Baseline and Post-Trial responses to anticholinergic side effects presented as color contours. Post-Trial, most subjects had none/mild side effects, with dry mouth and sleepy/tired symptoms significantly less post-trial, * $p<0.03$.

a. Rationale for the Study Purpose

The status quo for NB management in SCI is catheterization for safely emptying the bladder and anticholinergic medications once symptoms of DH or DSD occur.³ This does not address the pathologic reflexes that lead to morbidity, including AD. Neuromodulation via TTNS may be able to address DH and DSD and alter the course of NB and prevent the morbidity arising from pathologic reflexes secondary to SCI. Pilot trial have tested the safety and feasibility of TTNS in acute SCI and have generated evidence of efficacy, including mitigating the loss in bladder capacity seen in chronic SCI. Preliminary data of TTNS performed at home provides evidence of high compliance, feasibility, and efficacy. Unlike the clinic-based treatment required for PTNS, compliance for the home-based treatment with TTNS is nearly double that of PTNS based on pilot data.¹³

b. Rationale for Doses Selected

Based on our pilot trials, tibial nerve stimulation protocols use submotor current intensity with a duration of 200 μ s and frequency of 10Hz.¹⁰ TTNS will be used 5 days weekly.

c. Rationale for Study Population

Participants: Participants will include SCI performing intermittent catheterization (IC) and using OAB medications, ages 18-75. Adults over 75 years old are excluded as age-related changes may influence bladder function.¹⁹ Although NLUTD managed with an indwelling catheter could also benefit, the outcome measures in this study reflect areas of importance for those performing IC.

d. Rationale for Study Design

Based on our experience with TTNS, we believe this protocol can be used to help with neurogenic bladder management. Subjects who perform intermittent catheterization are being selected because they more likely to have incontinence than those with an indwelling catheter. If patients are interested, we will trial stimulation in clinic. We will exclude those who we cannot produce toe flexion with posterior tibial nerve stimulation.

After 2 weeks of home stimulation, those that are on bladder medicine will discontinue the medication. There is no other harm from rapid discontinuation of bladder medication, except for possible incontinence. The outcome measures are measure of bladder medication doses and surveys. The Incontinence Quality of Life (I-QOL) survey reflects the quality of life related to incontinence.²⁰ The Neurogenic Bladder Symptom Score (NBSS) measures and scores symptoms related to NGB.²¹ Both will be conducted at baseline and at 3-months post-discharge. The medication + TTNS adherence survey and Medication + TTNS % survey. Adherence scales will measure adherence to medication and transcutaneous tibial nerve stimulation. Will be conducted at baseline, then every 4 weeks. The Connor-Davidson Resilience Scale (CD-RISC-25) will measure resilience. Conducted at baseline, week 6 and at the end of trial. The PROMIS General Self-Efficacy (GSE) will measure self-efficacy. (There is no validated Spanish version. Therefore, a conclusion cannot be made.) Conducted at baseline, week 6 and at the end of trial.

2. HYPOTHESIS AND OBJECTIVES

1. Hypothesis

Specific Aim 1. In a randomized sham-control trial (n=60), determine the efficacy of home TTNS in SCI.

Hypothesis 1.1: Those in the TTNS group will be able to reduce their OAB medication dosages while maintaining continence compared to controls over a period of 3 months.

Hypothesis 1.2: Symptoms of NGB measured by the Neurogenic Bladder Symptom Score (NBSS) and a voiding diary (VD) will be reduced in the TTNS group compared to controls.

Specific Aim 2. Determine the impact on quality of life using TTNS at home.

Hypothesis 2.1: Incontinence-related QOL (I-QOL) will be increased in the TTNS group compared to the controls and from baseline.

Hypothesis 2.2: Anticholinergic side effects will be decreased in the TTNS group at 3-months compared to the controls and from baseline.

2. Primary Objectives

OBJECTIVE: to advance the science and care around bladder function and management among people with spinal cord injury/disease (SCI/D) and NLUTD with TTNS (and if so, we anticipate translating this research to other populations with NLUTD). Specifically, we seek to demonstrate that TTNS will improve NLUTD in SCI/D by:

1. intervening acutely with neuromodulation of the neurogenic bladder via TTNS to maintain bladder capacity by reducing pathologic reflexes, DH and DSD;
2. altering pathologic autonomic nervous system (ANS) responses and reducing autonomic dysreflexia (AD).
3. improving the quality of life (QOL) of those living with SCI/D by providing a feasible, non-pharmacologic, and dignified intervention for NLUTD that can be performed at home;

In this proposed study, we seek to provide evidence for overall objective #3 using home TTNS. We hypothesize that TTNS can be used in the home setting to maintain continence while reducing OAB medication dosages and improve quality of life.

Primary Objective 1: Evidence of TTNS efficacy with reduced OAB medication dosage

Primary Objective 2: Evidence of TTNS efficacy with reduced NGB symptoms as measured by the NBSS and the Voiding Diary

3. Secondary Objectives

Secondary Objective 1: I-QOL scores will be increased in the TTNS group compared to the controls

Secondary Objective 2: Anticholinergic side effects will be reduced in the TTNS group compared to the controls.

4. Potential Risks and Benefits:

a. End Points - Efficacy

Primary Objective 1: Evidence of TTNS efficacy with a greater proportion of bladder medication reduction in the TTNS group compared to the control group. Time to achieve this endpoint will be approximately 3 months after subject recruitment, anticipated 1 year to complete all subject recruitment.

Primary Objective 2: Evidence of TTNS efficacy with reduced NGB symptoms as measured by the NBSS and the Voiding Diary. Time to achieve this endpoint will be approximately 3 months after subject recruitment, anticipated 1 year to complete all subject recruitment.

b. End Points- Quality of Life

Secondary Objective 1: Improved QOL in the TTNS group compared to the controls at the end of the 3-month trial, based on I-QOL scores. Time to achieve this endpoint will be approximately 3 months after subject recruitment, anticipated 1 year to complete all subject recruitment.

Secondary Objective 2: Decreased anticholinergic side effects in the TTNS group compared to the controls at the end of the 3-month trial, based on an anticholinergic side effect survey. Time to achieve this endpoint will be approximately 3 months after subject recruitment, anticipated 1 year to complete all subject recruitment.

c. End Points - Safety

Urinary Tract Infection (UTI) risk:

We expect the rates of morbidity to be the same between those who participate and those who do not. However, because UTI is directly related to the bladder, we will focus on the occurrence of UTI. Based on literature, the overall rate of UTI in SCI is about 2.5 episodes per patient per year. As a result, we expect to see 0.6 episodes per patient during the 3-month study period. Based on that, we construct the stopping rules to stop at 20% UTI rate using lower 90% exact Blyth-Still-Casella confidence bounds. If the number of patients with UTI exceed 3 in the first 5 patients, 4 in the first 10 patients, or 5 in the 14 patients, then patient accrual will be paused pending a review by a medical advisory board comprised of SCI experts.

Bladder medication discontinuation risk:

- Worsened incontinence

Electric Stimulation Risks:

Electric stimulation is commonly performed on the extremities of those with spinal cord injury at the study institution. There are few adverse reactions to electric stimulation. The common ones include:

- Pain with electric stimulation: in these cases, the intensity is reduced until it is comfortable.
- Skin irritation: it is common for redness to occur on the skin at the site of the surface electrode. This typically dissipates within an hour of removing the electrode. In some cases, the redness remains the next day. In these cases, they are likely sensitive to the adhesive used and a hypoallergenic skin electrode will be provided.

3. STUDY POPULATION

1. List the number of subjects to be enrolled.

60 subjects. Consecutive SCI clinic encounters meeting the inclusion/exclusion criteria will be asked to enroll. Children and pregnant women will be excluded.

2. Criteria for Recruitment

- Initial screening will be performed in the clinic with the subject and PI
- In those interested, they will be given an IRB-approved consent form to review and to sign.
- Those with tetraplegia will unlikely have the ability to sign and we will have a 3rd party attest to the consent.
- Patients will ideally decide to participate in clinic, but can always decide at a later date and return to clinic to trial the TTNS as part of the I/E criteria.
- Flyers will be posted and distributed in the outpatient clinic to increase study awareness.

3. Inclusion Criteria (table 1)

Inclusion criteria: 1) ages 18-75 years; 2) SCI performing IC; 3) up to 2 anticholinergic OAB medications; 4) stable OAB medications in the past 2 months; 5) SCI neurologic level above T10; 6) English and Spanish speaking. Subjects that satisfy initial screening and willing to participate in the trial will have electric stimulation placed to attempt toe flexion as a check of the tibial nerve integrity. Those who cannot achieve toe flexion will be excluded.

Table 2. Inclusion and Exclusion Criteria

Inclusion Criteria	Exclusion Criteria
18-75 years old Traumatic and Non-traumatic SCI performing IC	Past history of genitourinary diagnoses or surgeries History of CNS disorders and/or peripheral neuropathy
Up to 2 anticholinergic OAB medications	Pregnancy
No changes in OAB medications	Lower motor neuron bladder
Neurologic level of injury above T10	Concern for tibial nerve pathway injury
English and Spanish speaking	Absence of toe flexion or AD with electric stimulation Bladder chemodenervation in past 6 months Potential for progressive SCI including neurodegenerative SCI, ALS, cancer myelopathy, Multiple sclerosis, transverse myelitis

SCI= spinal cord injury; IC= intermittent catheterization; OAB= overactive bladder; T10= thoracic level 10; CNS= central nervous system; AD= autonomic dysreflexia

4. Exclusion Criteria (table 1)

Subjects meeting any of the exclusion criteria at baseline will be excluded from participation:

- History of genitourinary diagnoses (i.e. prostate hypertrophy, overactive bladder, cancer, etc.)
- Potential for progressive SCI including neurodegenerative SCI, ALS, cancer myelopathy, Multiple sclerosis, transverse myelitis
- History of central nervous system disorder (i.e. prior SCI, stroke, brain injury, Parkinson's disease, MS, etc.)
- History of peripheral neuropathy
- pre-SCI symptoms of peripheral neuropathy (numbness and/or tingling in feet, sharp/jabbing/burning pain in feet, sensitivity to touch, lack of coordination, muscle weakness, etc.)
- Pregnancy
- Known injury to the lumbosacral spinal cord or plexus, or pelvis with associated neuropathy
- concern for tibial nerve pathway injury
- absence of toe flexion or autonomic dysreflexia during electric stimulation test
- bladder chemodenervation in prior 6 months

5. Withdrawal Criteria

Possible reasons for discontinuation of study intervention:

- Intolerable incontinence after discontinuation of bladder medications
- Intolerant to electric stimulation
- Non-compliance

To mitigate non-compliance, a stipend for effort in completing voiding diary will be provided at \$10 per day (2 days per month). An additional \$20 will be provided for logging bladder medication use and TTNS use/settings monthly. If both voiding diary and TTNS diary are reported, a \$10 bonus will be provided, therefore \$70 month 1, and \$50 for each months 2 and 3. At most per subject= \$170 for the 3-month trial per subject. Subjects will also receive reimbursement for travel for the urodynamic studies up to \$200 per trip (two urodynamic studies = up to \$400 per subject) and if medication reduction requires new prescriptions to cover co-payments when applicable up to \$50 total per subject.

6. Subject Replacement

Subjects who drop out will be replaced by recruitment from the SCI clinic and asking for informed consent from those who meet the I/E criteria.

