5. STUDY DESIGN

Anticipated number of patients to screen: 80

- Anticipated number of patients to enroll: 60
- Anticipated drop out or loss to follow-up: 6

Approximate time to complete study recruitment: 1 year

Expected duration of subject participation: 3-months. 3-months was selected as a fair assessment of efficacy. Clinically, medications are determined efficacious based on 1-month or less of use.

TTNS protocol: Same TTNS setting will be used as protocols HSC-MS-15-0806 and HSC-MS-17-0423. Electrodes 2 inch by 2 inch will be placed according to anatomic landmarks, with the negative electrode behind the internal malleolus and the positive electrode 10cm superior to the negative electrode, verified with rhythmic flexion of the toes secondary to stimulation of the flexor digitorum and hallucus brevis. The intensity level will be set to the amperage immediately under the threshold for motor contraction. If there is not contraction seen, patients will be excluded. In addition, if the patient perceives pain, the intensity will be lowered until comfortable. Stimulation frequency of 10 Hz and pulse width of 200ms in continuous mode will be used.^{13, 14}

Sham protocol and rationale: Toe flexion will be attempted, as in the TTNS protocol. Then the stimulation will be reduced to 1 mA for 30 minutes. Rationale: In order to make this a convincing blind, the TTNS protocol must be simulated closely as subjects may interact and discuss. Rather than turning the device off, they will be instructed that the stimulation required is below motor threshold, at 1 mA. Based on the knowledge of the pilot trial requiring about 40mA for TTNS, and the amperage for needle-driven PTNS adjacent to the tibial nerve at 0.5 – 1mA, it is unrealistic that 1mA via surface electrodes is sufficient to activate the tibial nerve. Both TTNS and sham participants will be instructed to use the device for 30 minutes, 5 days per week.

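### Eligibility does not screen for earlier tibial nerve stimulation, so people treated in the team's own home TTNS pilot could enter this sham-controlled trial

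*Combined protocol and SAP*

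**What the plan says.** Section 3 (Study Population) sets the target at 60 and describes the source: "Consecutive SCI clinic encounters meeting the inclusion/exclusion criteria will be asked to enroll". Clinic flyers supplement this, and dropouts are replaced from the same clinic. The only time-limited exclusion for an earlier bladder treatment is "bladder chemodenervation in prior 6 months". Neither Table 2 nor the bulleted list mentions earlier or current TTNS, PTNS or other neuromodulation, or participation in the two pilots. OAB medication must have been stable for 2 months.

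Section 1 describes Pilot Trial II as a "single-arm pre-post pilot trial in subjects with chronic SCI performing intermittent catheterization (IC) with complaints of incontinence". All 16 participants completed it, and 12 of 14 reduced their OAB dose. Section 5 carries the stimulation over unchanged: "Same TTNS setting will be used as protocols HSC-MS-15-0806 and HSC-MS-17-0423".

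The sham in section 5 runs at 1 mA, against about 40 mA needed in the pilot, and sham participants are told that 1 mA is the level required. The plan gives its reason for a close imitation: "In order to make this a convincing blind, the TTNS protocol must be simulated closely as subjects may interact and discuss". All participants record amperage in the bladder diary.

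Randomisation (section 6) is stratified by complete or incomplete SCI only. The covariates listed in section 11 do not include prior stimulation.

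**The concern.** The sham depends on participants accepting that 1 mA is a plausible treatment level. Someone who has used the active regimen at home may know otherwise, and the device setting and the diary both put the number in front of them. The plan treats conversation between participants as a threat to the blind, but does not consider participants who bring their own experience.

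Two things are at stake. The first is blinding. Reduction of OAB medication depends on what the participant tolerates, and the NBSS, I-QOL, side-effect survey and diary are self-reported, so knowledge of the arm can affect the outcomes. The schedule of events includes no check of blinding. The second is the baseline. A participant whose dose fell in the earlier pilot and then stayed stable for 2 months starts from a dose reached after TTNS, with less left to reduce.

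The plan already accepts that an earlier bladder treatment can carry over, because it excludes recent chemodenervation. It does not apply that reasoning to the treatment under test.

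**Working it through.** **1. Can a pilot participant qualify?** Pilot II and this trial line up as follows.

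| Feature | Pilot II (section 1) | This trial (sections 1, 3, 5) |
|---|---|---|
| Population | Chronic SCI on IC | Chronic SCI on IC |
| OAB medication | 14 in the dose-reduction denominator | Using OAB medication, up to 2 drugs, stable 2 months |
| Setting | Home | Home |
| Stimulation | HSC-MS-17-0423 | Same setting |
| Arms | Active only | Active or 1 mA sham |

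No exclusion bars a Pilot II participant as such. Someone fully weaned appears to be kept out, since sections 1 and 5 describe participants as using OAB medication, although the criterion itself states no minimum.

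**2. How many?** Pilot II completed 16, but the reduction is reported out of 14. The likely reading, which is an inference, is that 2 were not on medication. The Pilot II pool is then at most 14, less anyone fully weaned: 14/60 = 23% of the trial if every one returned. The documents do not give the size of Pilot I's active arm or the number of clinic patients with earlier PTNS.

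**3. The plan's own figure.** Section 11 gives 21 per group for 40% against 83%, two-sided 0.05, 80% power. The pooled normal formula, with mean proportion (0.40 + 0.83)/2 = 0.615, gives

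n = [1.96·√(2·0.615·0.385) + 0.84·√(0.40·0.60 + 0.83·0.17)]² / 0.43² = 18.9, so 19 per group.

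That is within 2 of the stated 21; the test behind 21 is not named. At 21 per group the same approximation gives power Φ[(0.43 − 1.96·0.150)/0.135] = 84%, which is the base below.

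**4. What returners could do.** Assumptions, not document figures: k of the 60 are returners, split evenly between arms, f = k/60. I show k = 4, 8 and the upper bound of 14.

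(a) *Inflation, TTNS effective.* Returners on sham never reduce; the active arm stays at 83%. Control rate = 0.40·(1 − f).

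(b) *Dilution.* Returners show no difference between arms. Difference = 0.43·(1 − f). Power is at 21 per group, and its range covers a common returner response from 0% to 83%.

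(c) *No true effect.* Everyone else responds at 40%, returners on sham at 0% and on TTNS at 83%. Spurious difference = 0.83·f. The last column is the chance of a significant result favouring TTNS at 21 per group, nominally 2.5%.

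| k | (a) control rate | (a) difference | (b) difference | (b) power | (c) spurious difference | (c) false positive |
|---|---|---|---|---|---|---|
| 0 | 40.0% | 43.0 | 43.0 | 84% | 0 | 2.5% |
| 4 | 37.3% | 45.7 | 40.1 | 77–79% | 5.5 | 5.5% |
| 8 | 34.7% | 48.3 | 37.3 | 69–73% | 11.1 | 11% |
| 14 | 30.7% | 52.3 | 33.0 | 58–63% | 19.4 | 24% |

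Differences are in percentage points. Each scenario is an extreme for the given k, and the k = 14 row also requires every eligible pilot participant to return.

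**The case against.** The strongest reply is that this is a possibility, not a shown event: no passage says that any pilot participant will be approached or will enrol. That stands, and it limits the weight of the point.

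Other replies also stand in part.

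- A reader might infer that all 16 Pilot II completers, 27% of the trial, could return. The 14-person denominator and the requirement to be using OAB medication make that unlikely.
- A reader might infer that 1 mA reveals the arm at once. The plan cites about 40 mA as the team's knowledge from a pilot it does not identify, and does not say what participants were told. Recognition is plausible for home users, but it is inferred.
- Feeling active-level stimulation is not special to pilot participants. Every candidate has the toe-flexion test, sham included. What former users add is knowledge of full sessions and usual settings. Any weakness of the sham in people new to TTNS is a separate matter that an exclusion would not cure.
- A reader might take one report of intolerance as ending the wean. Section 5 keeps the participant on the lowest tolerable dose and tries again the following week, so an assumption that unblinded sham participants never reduce is extreme.
- Pilot I was sham-controlled and in acute SCI, over 10 days, so its sham participants bring no experience of active treatment sessions.
- Randomisation balances prior exposure and baseline dose in expectation, and the mixed models adjust for OAB dosage. That answers chance imbalance in baseline dose. It does not address recognition of the sham, and the adjustment does not reach a simple comparison of proportions.

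**Conclusion.** The gap is real, and nothing elsewhere in the document closes it: prior stimulation is not an exclusion, a stratification factor or a listed covariate. It is a cheap improvement rather than a demonstrated flaw in the result.

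Its size is unknown because the number of returners is unknown. With 4 to 8 among 60, the extremes are a difference of about 46 to 48 points or about 40 to 37 points instead of 43. A figure above 50 points needs essentially all 14 to return and every sham returner to fail to reduce, so it is only a worst case.

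A reader might conclude that the plan is biased in favour of TTNS. The documents do not support a direction. Unblinded sham participants would inflate the difference, while participants with less dose left to reduce would dilute it.

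**What to change.** Add to the inclusion and exclusion text of section 3 and to Table 2 an exclusion such as: previous or current active tibial nerve stimulation (TTNS or PTNS), including active treatment in HSC-MS-15-0806 or HSC-MS-17-0423. Check it at screening against the pilot records. Limiting it to active treatment keeps Pilot I's sham participants eligible.

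If the exclusion is not adopted, record prior tibial nerve stimulation at baseline and prespecify in section 11 a sensitivity analysis of the primary endpoint without those participants.

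The cost is one eligibility line, a records check, and a small loss from the pool: likely no more than 14 from Pilot II, plus an unstated number from Pilot I's active arm and from PTNS, which Table 1 describes as largely unavailable. The plan expects to screen 80 to enrol 60, so the loss should be weighed against that margin of 20. The stated sample size does not change.
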